7.4 End of Study

At the end of the study, the parent will be asked to complete an eQuestionnaire to assess and comment on the usability of ClaimIt, the study chatbot and chatbot tools in general (Appendix II). Access to the study chatbot will be discontinued, and the study team may contact the parent if there are any outstanding study related queries.

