8.7 Tables, Figures, and Lists

8.7.1. Baseline characteristics and Usability Questionnaire

Tables of outputs from the proposed analysis are detailed in the TLF Deliverable Shell (see Section 10.2 for details). They are described below.

Table 1 outlines the baseline characteristics of both the respondents and infants in question. The mean age for respondents is reported with a standard deviation. Frequencies and percentages are reported for the following age categories: 21-25,

26-30, 31-35, 36-40, 41-45, and older than 45. Gender is reported for respondents as male and female.

Mean age for infants is also reported with standard deviations. Frequencies and percentages are reported for the following age categories: newborn (<1 month), 1 month, 2 months, 3 months, 4 months, 5 months, 6 months. Frequencies and percentages are given for both gestational age categories (premature (<37 weeks) and full-term (\geq 37 weeks)). Gender is also reported for infants as male and female.

Table 2 record the mean and standard deviation of Likert score responses as well as frequencies and percentages for questions 1, 2, 3, 4, 7, 8, 15, and 16 of the Usability of Chatbot and ClaimIt eQuestionnaire. Mean scores and standard deviations are reported as numbers to two decimal places. For example, if thirty of the forty mothers answered question one of the questionnaire as "Very easy" while ten of the participants answered "Easy", then the mean response value for that question would be 4.75 with a standard deviation of 0.44.

Table 3 reports the frequencies and percentages of responses to questions 5 and 6 of the Usability of Chatbot and ClaimIt eQuestionnaire which address whether or not the study chatbot malfunctioned (Yes or No) and whether or not the ClaimIt app malfunctioned. For each software malfunction, the participant is asked to report what happened. Their responses are recorded for all chatbot malfunctions in Table 4 and all ClaimIt malfunctions in Table 5.

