Tables 6-11 report open-ended answers to questions 9, 10, 11, 12, 13, and 14 of the Usability of Chatbot and ClaimIt eQuestionnaire. As nearly all answers to open-ended questions will be unique, all answers of a like theme will be recorded (for all intents as purposes) as the same answer. For example, if one respondent answers question 13 ("What did you like the most about the ClaimIt app?") by saying "I thought the app was easy to use", another answers "Easy to use", and another answers "Ease of use", then this answer will be reported as "Easy to use" (for example) with a frequency of three

(3). Any answers that are completely unique will be reported as such with a frequency of one (1).

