8.7.2. Analysis of Scripts

A series of analyses will be performed based on the Nutrition, Sleep, and Stress scripts administered to each participant. Results will be presented through figures and tables as appropriate.

Figures 1-21 are listed in the TLF deliverable shell. All figures will be in presented as bar charts and will provide enumerations of the categories detailed in their respective titles. Categorizations and subdivisions within each table are indicated by the word "by" in the title.

Tables 12-28 will present response frequencies to all open-ended questions within the scripts administered to each participant. Answers of the same theme will be compiled and presented as frequencies of the same answer as explained above in the example for Tables 6-11. Again any answers that are completely unique will be listed with a frequency of one (1).

All results from the analysis of chatbot scripts will be stratified by gestational maturity (preterm versus full-term) upon presentation.

9. Quality Control

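### SAP 8.7.2 counts repeated script answers with a rule made for a one-time questionnaire, so preterm/full-term theme counts also reflect how many parents and sessions each group contributes

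*SAP*

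**What the plan says.** SAP 8.7.2 describes two kinds of output for the chatbot scripts. For the tables, "Tables 12-28 will present response frequencies to all open-ended questions within the scripts administered to each participant". The counting rule follows: "Answers of the same theme will be compiled and presented as frequencies of the same answer", with a pointer back to the example for Tables 6-11. For Figures 1-21, "All figures will be in presented as bar charts and will provide enumerations of the categories detailed in their respective titles". Finally, "All results from the analysis of chatbot scripts will be stratified by gestational maturity (preterm versus full-term) upon presentation".

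The example it points to is in SAP 8.7.1 and concerns the usability questionnaire. Three respondents who make the same remark in different words are reported under one label "for example) with a frequency of three". That questionnaire is given once: "At the end of the study, the parent will be asked to complete an eQuestionnaire" (SAP 7.4).

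The scripts are different. SAP 7.1 schedules them three times a week over 28 days, with a maximum of 12 interactions per pair. The sleep script (Appendix II) also sends the parent back within a session to give further reasons for waking or for poor sleep.

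On denominators, "Table 3 reports the frequencies and percentages of responses to questions 5 and 6" (SAP 8.7.1), and Tables 1 and 2 also name percentages. The text for Tables 12-28 and Figures 1-21 names none. SAP 8.7.1 adds that "Tables of outputs from the proposed analysis are detailed in the TLF Deliverable Shell"; the shell is not among the documents reviewed.

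**The concern.** In Tables 6-11 a frequency of three means three people. Carried over to the scripts, it means three answers, which may come from three parents or from one parent on three days. SAP 8.4.1 intends to look at trends within and between subjects, and a pooled answer count cannot separate the two.

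The secondary objective is the preterm/full-term difference, and every script result is shown by that factor. If one group contributes more parents or sessions, its counts are higher even when the theme is equally common in both. The analysis sets allow unequal contribution:

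- FAS (8.2.2) needs only one completed topic.
- PP (8.2.3) needs seven interactions.
- Up to 10 dropouts are allowed for (8.1), with no stated split by group.

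What is at stake is how a descriptive contrast is read. No test, error rate or power is involved.

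**Working it through.** **Inputs from the documents**

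- 20 parents per group (SAP 6).
- Three sessions a week for 28 days, maximum 12 (7.1).
- Up to 10 dropouts (6.2.3, 8.1). A dropout is a non-compliant parent (8.1), meaning five or more consecutive sessions missed (7.3), so at most 12 - 5 = 7 sessions are completed.

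**Assumptions, because the documents give no figure**

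- The split of dropouts between groups.
- 1 to 7 sessions per dropout.
- 12 sessions for everyone else.
- The same theme rate p per session in both groups, and one mention per session at most.

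**1. The plan's own figure.** 3 x 28/7 = 12 sessions, which matches the stated maximum. A full group gives 20 x 12 = 240 parent-sessions.

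**2. Count and ratio.** Expected theme count = parent-sessions x p. With equal p, the ratio of counts equals the ratio of parent-sessions, whatever p is.

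**3. Dropout scenarios, no replacement.** With k dropouts in a group, each completing d sessions, parent-sessions = (20 - k) x 12 + k x d.

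| Split | d | Group with more dropouts | Other group | Ratio |
|---|---|---|---|---|
| 5:5 | any | equal | equal | 1.00 |
| 6:4 | 7 | 168 + 42 = 210 | 192 + 28 = 220 | 1.05 |
| 6:4 | 1 | 168 + 6 = 174 | 192 + 4 = 196 | 1.13 |
| 7:3 | 7 | 156 + 49 = 205 | 204 + 21 = 225 | 1.10 |
| 7:3 | 1 | 156 + 7 = 163 | 204 + 3 = 207 | 1.27 |

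**4. With replacement.** If all 10 are replaced within their group by parents who complete 12 sessions, parent-sessions = 240 + k x d. At 7:3 the direction reverses: 247/243 = 1.02 (d = 1) to 289/261 = 1.11 (d = 7), with the higher count in the group that had more dropouts.

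**5. PP limit.** If one group averaged 12 sessions and the other the floor of 7, the ratio would be 12/7 = 1.71. This is a bound, not an expectation.

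**6. Parents behind a count.** With one mention per session, a count of 12 can come from 1 parent (1/20 = 5%) or from 12 parents (12/20 = 60%).

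**7. What a denominator repairs.** Dividing by sessions asked returns p in both groups, a ratio of 1.0 in every equal-rate scenario above. The share of parents with any mention still rises with exposure. At an assumed p = 0.2 with independent sessions it is 1 - 0.8^7 = 79% after 7 sessions and 1 - 0.8^12 = 93% after 12.

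**8. What a pooled percentage does not repair.** Take invented rates: 7 parents per group at 50%, 13 at 20%, so the parent mean is (7 x 0.5 + 13 x 0.2)/20 = 30.5% in both groups. Let dropouts split 7:3, all from the 50% parents, 3 sessions each. The pooled percentages are (10.5 + 31.2)/177 = 23.6% and (4.5 + 24 + 31.2)/213 = 28.0%. If 7 parents are at 20% and 13 at 50%, with dropouts from the 20% parents, the order reverses: 82.2/177 = 46.4% and 89.4/213 = 42.0%. This shows only that a shift is possible, in either direction.

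**The case against.** The strongest objection is that the TLF shell holds the table layouts and becomes final when the SAP is executed (10.2), so units, group sizes and percentages may already be set there. That stands, and the finding is limited to what the SAP text specifies. For the figures, though, SAP 10.2 describes the shell as holding a list rather than mock-ups, so the titles would have to carry the unit.

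Missing percentages are weak evidence of intent, since Tables 6-11 also name none. This is also fair. The firmer evidence is the explicit pointer to a one-answer-per-person example.

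SAP 8.4 leaves the between-group measures to a later written agreement, so Tables 12-28 need not be the formal comparison. True, but they and the figures are the only script outputs the SAP describes, and they are stratified by group.

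Participation will be visible elsewhere: a withdrawal table and flow diagram (6.2.3), compliance reporting (7.3), and both FAS and PP outputs (8.4). This helps, but none of these summaries is said to be split by group or placed beside the counts.

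The sentence in 8.1 keeping dropouts' qualifying interactions refers to ITT, whereas the secondary outputs use FAS and PP. The point does not need that sentence: the FAS definition itself retains any enrolled parent with one completed topic.

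**Conclusion.** The point holds as a gap in the stated counting rule. Read as written, 8.7.2 yields counts that mix theme rate with participation, and no other section available here corrects this. Size, with equal rates: none if participation is balanced, about 1.05 to 1.13 for a 6:4 split of 10 dropouts, and about 1.10 to 1.27 for 7:3. These figures rest on assumed splits, 1 to 7 sessions per dropout, full completion by the rest, and no replacement.

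A reader might infer more than the documents support:

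- **That the groups will differ in participation, or that counts will be 1.71-fold apart.** Nothing indicates differential dropout, and 1.71 needs one group at the PP floor and the other at the maximum.
- **That raw counts have been chosen as the secondary endpoint.** SAP 8.4 says those variables are not yet defined.
- **That parent-level analysis is the only valid choice.** A session denominator already removes the scaling under equal rates, and the case for parent-level values rests on invented theme rates.

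Severity is minor to moderate: a descriptive pilot with no planned test, but the affected display bears directly on the secondary objective.

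**What to change.** In SAP 8.7.2, count a theme at most once per parent per session. Beside each count show, by group and for both FAS and PP:

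- the number and percentage of sessions containing the theme, out of sessions in which the question was asked;
- the number of parents with at least one mention, out of parents asked;
- sessions completed per parent.

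Using sessions asked also settles the denominator for questions reached only through a branch. State that the share of parents with any mention rises with sessions completed and is to be read with the session figures.

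A mean of parent-level shares, among parents asked the question, may be added as a sensitivity summary in case completion is related to the theme. Its weakness is noise from parents with few sessions: at a 20% rate with independent sessions, the SD of one parent's share is sqrt(0.2 x 0.8) = 0.40 for one session and sqrt(0.16/12) = 0.12 for twelve. None of these summaries corrects for sessions skipped on bad days.

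If the TLF shell already sets unit and denominator this way, state them in 8.7.2. Otherwise amend the shell under 10.2, which requires an SAP amendment and possibly a contract change. Beyond that, the cost is a few sentences and modest reprogramming; no new data are needed.

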9.1 Data and Output Quality Checks

All coding and results produced as part of this SAP will be reviewed for correctness and reproducibility via code review on primary, secondary, exploratory and baseline characteristics.

Parallel coding is not performed; however, all code developed by the Biostatistics

Department is reviewed and agreed upon iteratively for correctness and to ensure that all outputs meet the sponsor's specifications. All results are then reviewed by at least two members of the senior management team for quality control and interpretability.

Any issues identified during the code review will be documented and corrected until there are no issues. This will be done in order to safeguard against any errors, omissions, or deviation from the SAP. At the end of analysis, the raw output files and the final analysis datasets should be available and stored.

10. Reporting

10.1 Clinical Study Report

A Clinical Study Report will be developed and provided by ObvioHealth after the following have occurred: database lock, completed statistical analysis, and completed and client-approved TLF deliverable (through executed Tables, Listings, and Figures Deliverable Finalization Form). The report will review study background and methodology and will include all required results including all tables, listings, and figures agreed upon in the TLF Deliverable Shell (see Section 10.2 immediately below).

10.2 TLF Deliverable Shell

In conjunction with the finalized SAP, ObvioHealth and Danone will agree upon a set of tables, figures, and listings that will be provided as part of the final study deliverable – the TLF Deliverable Shell.

The TLF Deliverable Shell will consist of a set of spreadsheets (or in other words, a workbook) that houses the empty versions of all tables and listings for this study. The final worksheet in this workbook will be a list of figures to be delivered.

An executed SAP constitutes a written agreement on the TLF Deliverable Shell. As such, the most recent TLF Deliverable Shell will be versioned to 1.0 and considered final. Any additions to the final TLF Deliverable Shell after execution will require an amendment to the SAP and potential changes to the study contract.

11. References

- World Health Organization. (2017). Preterm birth. 2017 November [Accessed February 2, 2018]; Fact Sheet. Available from: http://www.who.int/mediacentre/factsheets/fs363/en/.
- 2. Fletcher, L., et al. (2017). *Parental Perception of Risk Associated With Their Premature Infant*. Adv Neonatal Care, 2017. **17**(4): p. 306-312.
- 3. Mughal, M.K., et al. (2017). *Parenting stress and development of late preterm infants at 4 months corrected age*. Res Nurs Health, 2017. **40**(5): p. 414-423.
- 4. Gondwe, K.W., et al. (2017). *Maternal Psychological Distress and Mother-Infant Relationship: Multiple-Birth Versus Singleton Preterm Infants*. Neonatal Netw, 2017. **36**(2): p. 77-88.
- 5. Polic, B., et al. (2016). Late preterm birth is a strong predictor of maternal stress later in life: Retrospective cohort study in school-aged children. J Paediatr Child Health, 2016. **52**(6): p. 608-13.
- 6. Rahman, A. M., Al Mamun, A., & Islam, A. (2017). Programming challenges of chatbot: Current and future prospective. *Humanitarian Technology Conference* (R10-HTC), 2017 IEEE Region 10: p. 75-78.

12. Appendices

Appendix I: Usability of Chatbot and ClaimIt eQuestionnaire

The following is a questionnaire is for you to	provide feedback o	on your	interactions	with th
chatbot. Please pick the best answer.				

nat	bot. Please pick the best answer.
1.	Please rate the study chatbot's overall ease of use on a scale of 1 to 5:
	(Very Difficult) 1 2 3 4 5 (Very Easy)
2.	Please rate the ClaimIt application's overall ease of use on a scale of 1 to 5:
	(Very Difficult) 1 2 3 4 5 (Very Easy)
3.	How satisfied were you with your interactions with the study chatbot?
	(Very Dissatisfied) 1 2 3 4 5 (Very Satisfied)
4.	How satisfied were you with your interactions with ClaimIt?
	(Very Dissatisfied) 1 2 3 4 5 (Very Satisfied)
5.	Did the study chatbot malfunction?
	a. Yes (will be asked a follow-up question)
	b. No
	(If Yes) How did the study chatbot malfunction? [Open-ended question]
6.	Did ClaimIt malfunction?
	a. Yes (will be asked a follow-up question)b. No
	(If Yes) How did ClaimIt malfunction? [Open-ended question]
7	How likely are you to consider using a chatbot application as an interactive tool to
, .	provide input on similar topics?
	(Not at all Likely) 1 2 3 4 5 (Very Likely)
8.	How would you rate the length of interactions you had with the study chatbot?
	(Too Long) 1 2 3 4 5 (Easily Manageable)
9.	What did you like the least about the study chatbot? [Open-ended question]
10.	What did you like the most about the study chatbot? [Open-ended question]
	Page 27 of 27

11.	Do you have any other comments about the study chatbot that you would like the investigators to know? [Open-ended question]
12.	What did you like the least about the ClaimIt app? [Open-ended question]
13.	What did you like the most about the ClaimIt app? [Open-ended question]
14.	Do you have any other comments about the ClaimIt app that you would like the investigators to know? [Open-ended question]
15.	How worried were you about sharing your data with the study chatbot? (Not at all worried) 1 2 3 4 5 (Very worried)
16.	How likely would you be to use a chatbot tool like this in real life to get access to information and reassurance if you could? (Not at all likely) 1 2 3 4 5 (Very likely)
	Why or why not? [Open-ended question]

Appendix II: Sleep Script

				How did you sl	How did you sleep last night?				
		Good				No	Not well		
Thanks for sharing that. How many total hours of night?	g that. How m	nany total hour night?	s of sleep did you get last	ou get last	Thanks for sh	Thanks for sharing that. How many total hours of sleep did you get last night?	any total ho night?	urs of sleep did	you get last
[Collect open ended numerical response and filter	ed numerical r	esponse and fi	lter into below categories]	:ategories]	[Collect open	[Collect open ended numerical response and filter into below categories]	onse and	filter into below	categories]
<7 hours	>7	≥7 hours	I don't know	know	<7 hours	≥7 hours		I don't know	know
		7	That's ok, I only need an estimate.	nly need an ate.		That is a good amount of	unt of	That's ok, I only need an estimate.	nly need an ate.
i m glad you still reel well-rested. Did anything affect your		I nat Is a good amount of sleep! Did anything bother you	[Collect open ended numerical response]	en ended response]	What do you think affected	sleep. Why do you feel like you didn't sleep well?	u feel p well?	[Collect open ended numerical response]	ded numerical nse]
sleep?		about your sleep?	Please share what may have affected your sleep last night.	what may I your sleep ight.	your steep:	bid anything bother you about your sleep?	nok Ja	Please share what may have affected your sleep last night.	hat may have eep last night.
			[All o	questions lead	[All questions lead to these responses]	[5			
			l woke u	I woke up during the night.	ight.				
I went 1	I went to bed too late.		Sorry to hear how often yo	Sorry to hear that, do you remember how often you woke up? [Collect open ended response]	emember ollect open	I woke up too early.	٠	Other	Nothing affected my
Sorry to hear that, what in particular kept you awake?	what in particu awake?	ular kept you		What wo	What would you say woke you up?	: you up?		What do you	Skip to question
I couldn't get to sleep	My baby	Other	I had to go to the bathroom	My baby	Physical discomfort	I had a lot on my on mind	Other	feel affected your sleep?	below]

Did it ta more t minutes slee	Did it take you more than 30 minutes to get to sleep?	Please share what happened with your	Please share what kept you		Please share what happened with your baby that kept you up.	Please share what made you feel physically uncomfortable (i.e. too hot, too cold, pain, etc.)	Please share what was on your mind.	Please share what kept you awake.	[Collect open ended response]	
	Yes	baby that kept you up.	awake.			[Collect open ended response]	l response]			
S O	How come?				Was there an	Was there any other reason you may have been awoken?	ı may have be	en awoken?		
					Yes					
) (Collec	[Collect open ended response]	[əsuods:	[Return to "N	Vhat would you above]	[Return to " What would you say woke you up ?" above]		No		
				Did anythin	Did anything else affect your sleep?	ur sleep?				
				Yes						
What e	lse affecte	What else affected your sleep? [Return to "What	eturn to "Wha	rt do you think	affected your sl	do you think affected your sleep?" responses above]	love]	0 Z		
		On a scale of 1	to 4 (1 being	Very Good and	4 being Very B	On a scale of 1 to 4 (1 being Very Good and 4 being Very Bad), how would you rate your quality of sleep last night?	u rate your qu	ality of sleep	last night?	
				1	[Collect open ended response]	ded response]				
			Thanks for		. How did you f	sharing that. How did you feel when you woke up this morning?	up this morr	ing?		
								Other		
	Ē	Tired		Well-rested	sted	How would yo	λυ describe hα	ow you felt wh	How would you describe how you felt when you woke up this morning?	this morning?
							ie [Colle	[Collect open ended response]	response]	
Did you s	still feel tir	Did you still feel tired in the afternoon?		s great! Did you fee afternoon?	That's great! Did you feel tired in the afternoon?	a l	Did you f	Did you feel tired in the afternoon?	e afternoon?	
				[All c	questions lead t	[All questions lead to these responses]				
				Yes					No	

			I'm glad to hear that! Would you like	some additional information on improving sleep quality overall?				No	
ır way?		ua.	Ç	2		I'm sorry to hear that. Would you find it helpful if we shared some additional information on improving sleep quality overall?			with me today!
Did you take a nap or manage being tired in any other way?		ou take? Other [Collect open ended response]			ON N	I'm sorry to hear that. Would me additional information o		proving sleep and sleep althy/510/sleep	Thanks for chatting with me today!
Did you take a nap or m	Medication	What medication did you take?	[Collect open ended response]	Did this help?			Yes	Great! This link has a lot of information about improving sleep and sleep quality: http://www.healthhub.sg/live-healthy/510/sleep	
		Nap Caffeine			Yes	I'm glad to hear that you're feeling less tired! Would you like some additional information on improving sleep quality overall?		Great! This link has a lot quality: http://w	

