7.1 Chatbot Interactions During Study Period

The parent will be asked to interact with the study chatbot three times a week (e.g., Monday, Wednesday and Friday [suggested schedule]) over a maximum 28-day period. During each of those interactions, they will be asked to interact on all three topics: sleep, stress, and infant nutrition. Reminder notifications will be sent via ClaimIt for any parent that does not interact with the chatbot per protocol.

The maximum number of interactions per subject pair is 12 (in total).

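### The sleep script asks about tiredness in the afternoon with only Yes or No as answers and no set session time, so an early session cannot give a valid same-day answer

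*SAP*

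**What the plan says.** The sleep script in SAP Appendix II starts with the previous night and then asks "How did you feel when you woke up this morning". Three waking states are offered: tired, well-rested and other. Each leads to an afternoon question. Parents who woke tired get "Did you still feel tired in the afternoon"; the others get "Did you feel tired in the afternoon". Every parent who reaches this point is therefore asked.

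The line after it reads "All questions lead to these responses", and the responses shown are Yes and No. A coping question follows, "Did you take a nap or manage being tired in any other way", with nap, caffeine, medication and other as choices and then a question on whether it helped. This fits only the Yes branch. The No branch answers "I'm glad to hear that! Would you like" and offers information on sleep quality. The same layout is printed again under the Appendix III heading.

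On timing, SAP section 7.1 (protocol section 10.2 is the same) asks parents to "interact with the study chatbot three times a week (e.g., Monday, Wednesday and Friday [suggested schedule". This suggests days but gives no hour. SAP section 7.5 and protocol section 10.6 let the parent start a conversation and, in certain instances, the chatbot. Again no hour is given.

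SAP section 8.7.2 counts the script answers by category, reports the open-ended ones as frequencies in Tables 12-28, and presents all script results by preterm versus full-term. No rule there uses the time of a session.

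**The concern.** The items run from last night to this morning to the afternoon, so the natural reading is the afternoon of the same day. A parent who chats before then is asked in the past tense about something that has not happened, and no answer shown says so.

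- **No** may mean not yet. It is stored in the same way as not tired, and the coping questions are not put.
- **Yes** may refer to the day before. The reported tiredness then precedes the night it is supposed to follow. The coping questions are put, but they may also concern the wrong day.

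Without the session time, the data cannot separate these meanings from valid same-day answers. At stake are the afternoon-tiredness item and the coping items that depend on it. The rest of the sleep record is not affected.

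**Working it through.** The plan states no figure on this point, so there is nothing to reproduce. The check sets the script against the scheduling text and then works out what can and cannot be said about size.

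**1. Reach of the item.** All three waking states lead to the afternoon question, so it is put in every completed sleep session. With 40 planned pairs (SAP section 8.1) and at most 12 interactions per pair (SAP section 7.1), the ceiling is 40 × 12 = 480 sessions, before any replacement of dropouts.

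**2. Share held early.** The documents do not give it. It can be anything from 0% (0 sessions) to 100% (480). As an assumption only, 10% to 50% would be 0.10 × 480 = 48 to 0.50 × 480 = 240 sessions.

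**3. Effect on the recorded rate.** Let p be the true rate of afternoon tiredness, e the share of early sessions, and y the share of early sessions answered Yes.

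- Recorded rate = p(1 − e) + y·e
- Bias = e(y − p)

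The bias is zero if y = p. If no early parent says Yes (y = 0), the shortfall is p × e. If y exceeds p, tiredness is over-recorded.

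None of the values below comes from the documents. Take p = 60%.

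| Early share e | Recorded if y = 0 | Recorded if y = 30% | Recorded if y = 60% |
|---|---|---|---|
| 20% | 0.6 × 0.8 = 48% | 0.48 + 0.3 × 0.2 = 54% | 60% |
| 30% | 0.6 × 0.7 = 42% | 0.42 + 0.3 × 0.3 = 51% | 60% |
| 50% | 0.6 × 0.5 = 30% | 0.30 + 0.3 × 0.5 = 45% | 60% |

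**4. Effect on the group comparison.** If both groups have the same p and the same y, the false gap is (p − y) × (difference in e). With e = 20% in one group and 50% in the other:

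- y = 0: 0.6 × 0.3 = 18 points
- y = 30%: 0.3 × 0.3 = 9 points
- y = 60%: 0 points

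If e and y are both the same in the two groups, equal true rates stay equal. A real difference between p₁ and p₂ would then be shrunk to (p₁ − p₂)(1 − e), but no false one would appear.

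**5. Effect on coping.** The coping questions are put only after a recorded Yes, so their denominator moves with the recorded rate in step 3.

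**The case against.** The case on the other side has real weight.

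**Silence is not permission.** A reader might infer that the plan allows sessions at any hour. Neither document says so. Parents receive navigation instructions and an overview of notifications, and a prompt time could be set there. The past tense of the script would suit late-day use. This stands as a limit on certainty, but the protocol and SAP still contain neither a time nor a rule for early sessions.

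**Early sessions need not lose the coping items.** A reader might infer that every morning session skips them. Only a No does. For a parent chatting in the morning, afternoon coping has not yet occurred, so not asking about it is not itself a false record. This stands. What remains is the ambiguous No, any coping earlier in the day that goes unasked, and a Yes of uncertain date.

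**The answer set may be wider than it looks.** The table is broken, the chatbot is described as conversational, and the sleep-hours item has a path for parents who do not know. A typed reply of not yet might therefore appear in a transcript, and monitors review transcripts for completeness and consistency (protocol sections 10.7 and 13.1). This is a partial safeguard. It does not provide a category for that reply, and a plain No would raise no query.

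**The size is easily overstated.** A reader might take the 18-point gap in the illustration as an estimate. It needs every early parent to answer No, which is least plausible for those who have just said that they woke tired. It also needs session times to differ by gestational group, for which the documents give no reason. This objection stands in full.

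**Materiality is limited.** This is one item within one of three topics, in a descriptive pilot of 40 pairs whose primary endpoint is obtaining records. The secondary variables are not yet defined (SAP section 8.4), and the figure titles sit in a shell that is not part of the documents. No planned comparison of afternoon tiredness can be shown. The open-ended coping answers, however, fall within Tables 12-28 and are presented by group.

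**Conclusion.** The point holds for the afternoon-tiredness item and the coping items behind it. As written, a session held before the afternoon cannot give a valid same-day answer, and nothing in the SAP identifies such sessions.

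The size cannot be computed. The early share lies between none and all of at most 480 sessions. Under-recording lies between zero and p × e, the upper end resting on the worst-case assumption that all early answers are No. A false preterm versus full-term difference needs session timing or early answering to differ between the groups, and the documents give no evidence that either does.

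The conclusion assumes that the extracted Yes/No layout is complete and that no session time is fixed in materials outside these two documents.

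**What to change.** - **Script, if it can still be changed:** add an answer to this item meaning that it is not afternoon yet.
- **Analysis, in either case:** report afternoon tiredness and coping only from sessions whose time stamp falls after the afternoon, or flag the earlier ones. Fix the cut-off time in the SAP before the data are examined.
- **Reporting:** tabulate session time by preterm and full-term group, so that a reader can see whether timing differs.
- **Data:** confirm that the transcript export keeps the time stamp; neither document says that it does. If a prompt time already exists elsewhere, state it in the SAP.

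Do not confine all sessions to late afternoon to protect this one item. A narrower window could lower completion of all three topics, which is the primary endpoint. Five consecutive missed sessions also count as non-compliance and hence dropout (SAP sections 7.3 and 8.1).

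The cost is one answer option, one filter and one table. The downside is that fewer sessions contribute to the tiredness and coping outputs.
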